8.3. Loss to Follow Up

There will be no protocol-dictated interventions to improve patient compliance besides what physicians do in practice. This study will use an innovative electronic data capture approach (e.g. Smartphone APP), which is expected to minimize the data collection burden and reduce patients' loss to follow up.

9. STATISTICAL CONSIDERATIONS

9.1. Sample Size Determination

9.1.1. Hypotheses

No formal hypotheses will be tested, as this will be a descriptive study. The objective of this study is to observe the effectiveness and safety among Chinese CHB patients who receive long-term TDF treatment in real-world setting.

9.1.2. Sample Size Assumptions

Sample sizes are estimated based on feasibility and precision level achieved as no formal hypothesis will be tested in this study.

The primary objective of this study is to assess the effectiveness of TDF, with one important indicator being the proportion of subjects who achieve the CVR (i.e. HBV-DNA undetectable) at weeks of 48, 96, and 144. To be able to assess the CVR achievement at week 144, a sample size of 2,000 patients will provide a precision of no more than 2.2%, assuming the percentage of patients achieving CVR is 80% and the rate of loss-to-follow-up and discontinuation is 35%. The precision is calculated by the following: precision = $Z_{(1\alpha/2)}$ *SQRT(p*(1-p)/N), where Z is the critical value of normal distribution corresponding to the probability of 1- α /2 (corresponding to (1- α)*100% confidence interval), and p is the percentage of patients achieving CVR. It is half of the width of 95% confidence interval for the point estimate, which means that the lower and upper bounds of the 95% confidence interval for the patient proportion of interest will be within 2.2% of the point estimate (point estimate +/- 2.2%). In addition, there will be approximately a 73% probability of identifying a least one AE with a true AE rate of 0.1%.

For an exploratory purpose, more calculations about the precisions of evaluating the CVR achievement percentage are also provided for difference sub-populations, such as HBeAg positive or Cirrhosis. Assuming HBeAg positive (Cirrhosis) is made of 54.5% (20%) of HBV patients, the percentage of patients achieving CVR is 80% and 3 -year drop-out rate is 35%, a sample size of N=2000 will have 1090 (400) patients in the interested group and about 708 (260) completers and a precision of no more than 0.029 (0.049) [You, 2016].

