The effectiveness and renal safety results of TDF varies between registered clinical trials [complete virological response (CVR) over 95%] and real-world research (CVR approximately 71 to 92%) [Pol, 2012, Idilman, 2015, Kim, 2015], partly due to the difference between clinical trial patient population and real world study population. Phase III clinical trials are conducted under well-controlled conditions among pre-selected patients with strict in/exclusion criteria, generally eliminating older patients and those with co-infections or comorbidities (such as cirrhosis). Compared with most patients seen in real world practice, those participating in clinical trials are typically younger and healthier with less comorbidity and better treatment adherence. Understanding how antivirals perform in real world general patient population is more important to guide routine clinical practice. The results from high-quality real-world cohorts will continue to provide clinical guidance for physicians by providing safety and effectiveness evidence across diverse treatment settings and in a broader array of patients and enable more patients to benefit from the available treatment options.

Lampertico et al. [Lampertico, 2016] reviewed recent real-world evidence on the safety of TDF treatment among HBV-monoinfected patients. Overall, TDF can lead to minor reduction in eGFR and BMD, which was mainly observed during early stage of treatment and remained stable in long-term follow up in most patients. Although TDF was well tolerated with no clinically significant renal toxicity, evidence from cohort studies seems to be conflicting. Reductions in GFR/Creatinine among HBV patients treated with TDF were reported, the clinical significance of these changes needs more discussion and the degree of association between TDF and changes in renal function indicators varies across studies. The inconsistency might result from small sample size, different baseline population with different renal function, varying measures of renal function. Few studies observed BMD during TDF treatment among CHB patients. Gill et al. carried out a single-centre cohort study in the UK, specifically to assess the impact of TDF on BMD in 170 HBV-monoinfected patients. There was no difference in T-score between treatment groups for lumbar or femoral neck measures, but TDF was associated with a lower hip T-score compared with no TDF (P = 0.02) [Gill, 2015].

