5. STUDY DESIGN

5.1. Overall Design

This is a China-based multi-center, prospective, longitudinal, real-world study, taking a naturalistic approach, capturing real-world medical practice and patient outcomes using a non-interventional design. Patients with diagnosed CHB who newly initiate and continue TDF monotherapy or combination therapy will be consecutively recruited from general and specialized hospitals across China. Site/hospital selection will consider geographic and hospital type/tier representativeness, investigators' research interest, as well as feasibility such as electronic data collection approaches. For non-enrolled subjects, reasons of exclusion will be collected.

During the study, patients will seek and receive medical care as they do in regular clinical practice setting without investigational product tested. Specifically, patients' diagnosis, treatment, and monitoring will be left to their physicians' routine practice without study-

dictated visits and procedures. Minimal patient evaluations will be done by physicians, e.g. baseline patient demographics and clinical characteristics and patients' treatment adherence. Minimal lab tests in line with routine clinical practice (HBV DNA, serum creatinine, and serum phosphate) will be conducted in a central lab on the basis of the judgement of treating physicians and willingness of patients.

Other patient data will be collected using electronic approaches, mainly from lab test reports or medical records at the entry of this study and thereafter at 6-month intervals for 3 years. As this is a real-world study without mandatory scheduled visits, patients may not seek medical care and conduct assessments (e.g. lab tests) exactly at 6-month intervals. The 6-month interval is set to remind investigators to collect data regularly.

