7. STUDY ASSESSMENTS AND PROCEDURES

Given the naturalistic nature of the study design, all participated patients will be diagnosed, treated, and monitored as in real clinical practice according to their physicians' judgement without additional interventions and procedures. Protocol-specified information relevant to CHB diagnosis and treatment will be collected from assessments generated from routine clinical care, including lab tests and medical records, complemented with investigators' evaluation at the entry of this study and thereafter at 6-month intervals for up to 3 years until the end of the study or until participant withdraws from this study. It is expected that diagnosis and treatment practice will vary across study hospitals and physicians.

Data will be collected using an innovative electronic approach, i.e. Smartphone App, with the intention to reduce the data collection burden on patients, investigators, and sites and also improve data collection efficiency and quality. The use of Smartphone App enables patients and investigators to upload lab tests and medical records and complete brief online evaluations (e.g. whether the patient remains on TDF? Any changes on TDF treatment?) via their smartphones.

There are no mandatory visits during the study period, however, according to the CHB clinical practice and CHB management guideline, CHB patients on anti-viral treatment should be monitored for at least every 6 months, e.g. HBV DNA, liver and renal function. Data collected and their timing are summarized in the SoA (See Section 2). The 6-month data collection interval is set to remind investigators to collect patient's data regularly. A minimal necessary medical evaluation in line with routine clinical practice following the guideline recommendation is required for all eligible patients at the entry of study for basic medical assessment on the basis of the judgement of treating physicians and willingness of patients. Other lab tests and procedures in the SoA will be judged by the treating physician and carried out by patients. Only available and identifiable assessments will be collected.

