9.3.3. Secondary Analyses

Patients' renal functional change during TDF treatment period will be explored.

- The proportion of patients whose eGFR (MDRD equation) decline >20% from baseline at weeks of 48, 96 and up to week 144 will be summarized for the overall study analysis population and sub-group populations.
- Mean and 95% confidence intervals for the change from baseline in eGFR values will be calculated for the overall analysis population, as well as for the subpopulations of interests. A mixed effect model will be fitted to explore the impacts on the mean change from baseline in eGFR of fixed effects of age, gender, treatment-naïve or experienced, ADV or non-ADV, type of baseline comorbidities (Cirrhosis, Hypertension, diabetes mellitus (DM), non-overlapping), baseline eGFR values, baseline HBV-DNA counts, baseline HBeAg status, and other factors as appropriate, and random effects of subject ID.
- The percentage of change from baseline in eGFR will be estimated for the overall analysis population and by sub-populations at weeks 48, 96, and 144. Figures of mean eGFR values overall and the sub-populations of interests will be generated.
- The proportion of patients with confirmed a serum phosphate Grade 3 or 4 abnormality (<2.0 mg/dL) at weeks of 48, 98 and 144 will be summarized for the overall study analysis population and sub-group populations.
- The percentage of change from baseline in serum phosphate will be estimated for the overall analysis population and by sub-populations at weeks 48, 96, and 144. Figures of mean serum phosphate values overall and the sub-populations of interests will be generated.
- Mean and 95% confidence intervals for the change from baseline in serum phosphate values will be calculated for the overall analysis population, as well as for the sub-populations of interests. A mixed effect model will be fitted to explore the impacts on the mean change from baseline in serum phosphate of fixed effects of age, gender, treatment-naïve or experienced, ADV or non-ADV, type of baseline co-morbidities (Cirrhosis, Hypertension, DM, non-overlapping), baseline eGFR values, baseline HBV-DNA counts, baseline HBeAg status, baseline phosphorus and other factors as appropriate, and random effects of subject ID.

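### The planned 2.2-point precision for week-144 CVR assumes independent patients, so it holds only if hospital clustering is negligible; the number of sites and the ICC are not stated

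*Protocol*

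**What the plan says.** Protocol section 9.1.2 bases the sample size on feasibility and precision. For CVR at week 144 it states that "a sample size of 2,000 patients will provide a precision of no more than 2.2" per cent. Two conditions are attached: "assuming the percentage of patients achieving CVR is 80" per cent, and "the rate of loss-to-follow-up and discontinuation is 35" per cent. Precision is the normal critical value times the square root of p(1−p)/N, and the text explains that "It is half of the width of 95% confidence interval for the point estimate". Table 3 in 9.1.3 repeats 0.022 for 2,000 enrolled and 1,300 completers. It varies the total sample size only; CVR stays at 80% and dropout at 35%.

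On the sampling structure, section 5.1 says that patients "will be consecutively recruited from general and specialized hospitals across China". Section 7 adds: "It is expected that diagnosis and treatment practice will vary across study hospitals and physicians".

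On analysis, the mixed models for change in eGFR and in serum phosphate (9.3.3) list named fixed effects and then "other factors as appropriate, and random effects of subject ID". No hospital term is named. Section 9.3.2 says the CVR proportions will be summarised but names no interval method. Section 9.3.4.2 foresees a generalized linear mixed model for CVR and leaves its details to the RAP.

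**The concern.** The formula in 9.1.2 is valid when each patient contributes independent information. Patients treated in the same hospital share referral patterns, case mix, prescribing habits and follow-up practice. If CVR differs between hospitals for such reasons, two patients from one hospital tell us less than two from different hospitals, and the variance of the overall proportion rises by the design effect. The protocol expects practice to differ between hospitals, yet its precision statement allows nothing for this, and its sensitivity table does not test it.

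The study tests no formal hypothesis (9.1.1), and its size is justified by precision. A half-width that is too favourable would overstate how firmly the study can fix the CVR rate it wants to offer as clinical guidance. The same applies to the subgroup precisions of 0.029 and 0.049 in 9.1.2, which use the same formula, and to the renal models if hospital is left out.

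**Working it through.** **Inputs from the protocol.** N = 2,000, CVR p = 0.80, dropout 35%, 95% confidence (z = 1.96), all from 9.1.2. Completers: 2,000 × 0.65 = 1,300.

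**Reproducing the stated figure.** 1.96 × sqrt(0.80 × 0.20 / 1300) = 0.0217, or 2.17%, which rounds to the stated 2.2%. The arithmetic is right. The margin below 2.2% is very small.

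**Inputs that the protocol does not give.** The number of hospitals K and the ICC for CVR are assumptions here. For K, section 6 reports that most physicians surveyed for feasibility thought they could recruit over 50 patients each in three months. At 50 per site, 2,000 patients need 2,000/50 = 40 sites, hence m = 1300/40 = 32.5 completers per site. I also show K = 17 (the number of hospitals in the feasibility survey, not a planned site count) and K = 100. ICC values of 0.01, 0.02 and 0.05 are illustrative. Site sizes are taken as equal.

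**Formula.** Design effect DE = 1 + (m − 1) × ICC; half-width = 2.17% × sqrt(DE).

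| Sites K | Completers per site m | ICC 0.01 | ICC 0.02 | ICC 0.05 |
|---|---|---|---|---|
| 100 | 13.0 | 2.30% | 2.42% | 2.75% |
| 40 | 32.5 | 2.49% | 2.78% | 3.49% |
| 17 | 76.5 | 2.88% | 3.44% | 4.75% |

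At 40 sites:
- DE is 1 + 31.5 × 0.01 = 1.315, 1 + 31.5 × 0.02 = 1.63 and 1 + 31.5 × 0.05 = 2.575.
- The effective number of completers, 1300/DE, is 989, 798 and 505.
- An interval that ignored this clustering would cover about 91%, 88% and 78%, from 2Φ(1.96/sqrt(DE)) − 1, with hospitals regarded as a sample from a wider set.

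**How small must the ICC be?** Setting 2.17% × sqrt(DE) ≤ 2.2% gives ICC ≤ ((0.022/0.02174)² − 1)/(m − 1). That is about 0.0003 at 17 sites, 0.0008 at 40 and 0.002 at 100. At 40 sites it corresponds to a between-hospital SD in CVR of sqrt(0.00075 × 0.16) = 0.011, about 1 point. If anything up to 2.25% counts as 2.2%, the limit at 40 sites is ICC 0.0022, an SD of about 1.9 points. For comparison, ICC 0.02 is an SD of sqrt(0.02 × 0.16) = 5.7 points.

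**Sensitivity to CVR.** Section 3.2 cites "real-world research (CVR approximately 71 to 92" per cent. Without clustering, the same formula gives 1.96 × sqrt(0.71 × 0.29 / 1300) = 2.47% at the low end and 1.96 × sqrt(0.92 × 0.08 / 1300) = 1.47% at the high end.

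**The case against.** The strongest reply is that no shortfall has been demonstrated. The protocol gives no ICC and no site count. Section 7 says practice will vary, not that CVR will. Every patient is on TDF, those who stop for at least 28 days are withdrawn (8.2), and HBV DNA is measured in a central laboratory, which removes assay differences between sites. With 100 sites and ICC 0.01 the half-width is only 2.3%. Much of this stands: the size of the effect is unknown and could be trivial. But the central laboratory does not remove differences in case mix, earlier NUC treatment, adherence or use of combination therapy, and the protocol gives no reason to expect hospitals to agree within a point or two.

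A reader might infer that the final confidence intervals will be too narrow. The document does not support that. The interval method for CVR is not fixed, and the RAP could use clustered variance. Only the planning figure is shown to ignore clustering. Likewise, only the two renal models are fixed with a subject effect alone, and their open list of further factors might admit hospital as a fixed effect. The random effects of the CVR model are not stated.

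A reader might also infer that the 2.2% limit fails because CVR could be 71%. It does not fail: the statement is explicitly conditional on 80%, and at 92% the half-width is smaller. Nor is the interval the only inferential output, since 9.3, 9.3.3 and 9.3.4.2 plan subgroup tests, mixed models, log-rank tests and Cox regression.

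Finally, sites are chosen partly for investigator interest and feasibility, so there is no probability sample of hospitals, and treating hospitals as random is a modelling choice. That is a fair limit on the coverage figures. It does not justify leaving the independence assumption unstated.

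**Conclusion.** The point holds in conditional form. The 2.2% is correctly calculated under its stated 80% CVR and 35% dropout, but it also rests on an unstated third assumption, that patients within a hospital are no more alike than patients from different hospitals. With 2.17% against 2.2%, there is almost no room for that to be wrong. Under illustrative ICCs of 0.01 to 0.05, the half-width would be 2.5 to 3.5 points at 40 sites, and about 2.3 to 4.8 points across 100 down to 17 sites. These ranges depend on assumed site numbers, ICCs and equal site sizes; none of them is a corrected value.

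This is a gap in the planning assumptions and in the specification of the renal models, not an arithmetic error and not proof that the precision will be missed. It affects claimed precision and coverage, not the power of a primary test, because there is none. It is worth correcting because the remedy is cheap.

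**What to change.** - In 9.1.2, state that 2.2% assumes 80% CVR and no clustering by hospital.
- In 9.1.3, add a sensitivity table of the half-width over the planned number of sites, an assumed ICC range and CVR from 71% to 92%, with the source or reasoning for the ICC range.
- Specify that confidence intervals for proportions and for mean changes use hospital-clustered (robust) variance. If sites are few, use a t reference with sites minus one degrees of freedom.
- In 9.3.3, add a hospital random intercept to the eGFR and phosphate mixed models, alongside the subject effect.

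The cost is wording, a less favourable stated precision, and somewhat wider intervals where clustering is present. No additional patients, visits or data items are needed beyond the identity of the recruiting hospital.

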9.1.3. Sample Size Sensitivity

Different sample sizes and corresponding precisions are provided in the Table 3 below. It assumes the percentage of patients achieving CVR is 80%, and the drop-out rate is 35%.

Table 3 Different Sample Sizes and Corresponding Precisions

Total Sample Size (N)	Completers after 35% drop out	Precision (Half width of 95% confidence interval)
3000	1950	0.018
2500	1625	0.019
2000	1300	0.022
1500	975	0.025
1000	650	0.031
750	488	0.036
500	325	0.043

9.2. Populations for Analyses

The main population for analyses will consist of all consented participants who have the requested baseline data and at least one post-baseline assessment data.

9.3. Statistical Analyses

A detailed Reporting and Analysis Plan (RAP) outlining details of data analyses will be created and described below. Besides the 144-week analysis, key analyses may be conducted annually with the 48-week and 96-week cut-off data to look at short-term patient outcomes. No adjustment for multiplicity will be made for these analyses.

Continuous variables will be summarized for overall population and various subgroups using mean (standard deviation) and/or median (range), while categorical variables will be summarized in tables of frequencies and percentages. Comparative analyses will be performed across sub-groups using Student's t test or analyses of variance for quantitative variables, and Pearson's Chi-square test (Fisher exact test might be used when necessary) for qualitative variables. Nonparametric tests will be used when necessary.

In primary and secondary analyses, as this is a real-world study without mandatory scheduled visits, the assessments (e.g. lab test) may not be conducted exactly at 6-month intervals, but to keep the robustness of the estimation for effectiveness and renal function change, a time window that ± 28 days for week 48, 96 and 144 will be applied in each cut-off analyses. As the supportive analyses, the analyses with time windows that ± 3 months will be conducted. More details will be included in Reporting and Analyses Plan (RAP).

9.3.1. Baseline Description

Among eligible patients approached by investigators or site staff, the proportion who agreed to participate this study will be estimated. The basic socio-demographic and health status information will be summarized and compared between those who were enrolled and those who refused to participate to examine the potential difference between the two groups of CHB patients., a brief screening survey will be administered to all eligible patients (including non-enrolled patients) to collect a minimal amount of socio-demographic and health information. This is to enable the evaluation of possible patient selection bias and potential confounding factors in study analysis. All individual identifiers will be removed for non-enrolled patients., a brief screening survey will be administered to all eligible patients (including non-enrolled patients) to collect a minimal amount of socio-demographic and health information.

For the analysis population, baseline patients' characteristics (e.g. socio-demographic, clinical, and genotype) will be summarized using descriptive statistics for the overall population and by subgroups (e.g. gender, age group, clinical characteristics).

9.3.2. Primary Analyses

In order to evaluate the effectiveness of TDF for the treatment of CHB patients, the following estimates will be summarized for the overall analysis population and subpopulations (e.g. gender, age group, clinical characteristics).

- The proportion of patients who achieve CVR at week of 144
- The proportion of patients who achieve CVR at weeks of 48 and 96
- The proportion of patients who achieve HBeAg loss and/or HBeAg seroconversion in HBeAg positive patients at weeks of 48, 96, and 144
- The proportion of patients who achieve HBsAg loss and/or HBsAg seroconversion at weeks of 48, 96, and 144
- The proportion of patients who achieve transaminase normalization at weeks of 48, 96, and 144

Sub-groups are defined according to patients sociodemographic, lifestyle and clinical characteristics and on treatment factors, including age, gender, baseline HBV DNA level, HBeAg status, baseline alanine aminotransferase level in relation to the upper limit of the normal range, receipt or no-receipt of previous treatment with other NUCs, previous history of drug resistance, baseline genotype, comorbidities (cirrhosis, hypertension, diabetes, renal disease), patient treatment adherence.

A time window that ± 28 days for week 48, 96 and 144 will be applied in each cut-off analyses. As the supportive analyses, the analyses with time windows that ± 3 months will be conducted.

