3.2. Rationale

TDF was approved for the treatment of CHB in the U.S. in 2008 and in China in 2013. TDF is recommended as the first line anti-viral therapy either for naïve patients or as a rescue regimen by CHB clinical practice guidelines based on its high potency in supressing HBV DNA, good tolerance profile and low incidence of drug resistance [Chinese Medical Association, 2015, Sarin, 2016, Terrault, 2016, EASL, 2017]. Two global registered multicentred, randomized, controlled Phase III studies, GS-US-174-0102 (NCT00117676; Study 102) and GS-US-174-0103 (NCT00116805; Study 103), have shown that, during 48 weeks of TDF treatment period, 76.0% hepatitis B envelope antigen (HBeAg) positive and 93% HBeAg negative CHB patients achieved complete viral suppression (defined as HBV-DNA<69IU/ml, 400copies/ml) [Marcellin, 2008]; 98.0% and 99.6% achieved complete viral suppression among HBeAg positive and HBeAg negative respectively during 8 years of treatment [Marcellin, 2014]. No cases of TDF drug resistance were observed through the 8 years of treatment [Corsa, 2015]. The 48-week Chinese multicentred, randomized, controlled Phase III trials showed similar reports and the following open-label study up to 192 weeks reported similar results [Hou, 2015, Hou, 2016].

Besides the high potency of TDF in viral suppression, TDF was well-tolerated in the 8-years follow-up studies 102 & 103 [GS-US-174-0102 and GS-US-174-0103) and 192-week follow-up Phase III study from China [Hou, 2016]. For Studies 102 & 103, no renal toxic effects were observed during the 48 weeks of TDF treatment among patients with CHB who had preserved renal function at baseline; and the incidence of all individual renal adverse events in the 8-year follow up period was reported $\leq 2.2\%$ (either ≥ 0.5 mg/dL increase in serum creatinine, or serum phosphate ≤ 2 mg/dL, or creatinine clearance ≤ 50 mL/min). Nearly 1% of renal adverse events was observed in the long-term follow up period in the Chinese Phase III study [Hou, 2016]. In TDF global registry study, BMD was also monitored, it was observed that T scores of hip and spine were stable between years 4-8.

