4. OBJECTIVES AND RESEARCH QUESTIONS

Study objectives and research questions are listed in the Table 2.

Table 2 Objectives and Research Questions

Objectives	Research Questions
Primary Objective To assess the effectiveness among overall and sub-group Chinese CHB patients who receive TDF treatment in real-world	Among the overall analysis population and relevant sub-group* populations: • Proportion of patients who achieve complete virologic response (CVR) at
	 weeks of 48, 96, and 144. Proportion of patients who achieve HBeAg loss and/or HBeAg. seroconversion in HBeAg positive patients at weeks of 48, 96 and 144.
	 Proportion of patients who achieve HBsAg loss and/or HBsAg seroconversion at weeks of 48, 96 and 144.
	 Proportion of patients who achieve transaminase normalization at weeks of 48, 96 and 144.
	 Time to CVR, defined as time from baseline to the first occurrence of CVR (if applicable)
Secondary Objective	
To assess the renal function change among overall and sub-group CHB patients during TDF	Among the overall analysis population and relevant sub-group* populations:
treatment	 Proportion of patients whose eGFR decline >20% from baseline at weeks of 48, 96,

Objectives	Research Questions
	and 144.
	 Percentage of change from baseline in eGFR at weeks of 48, 96, and 144
	Change from baseline in eGFR values at weeks of 48, 98 and 144
	 Proportion of patients with confirmed serum phosphate Grade 3 or 4 abnormality (<2.0 mg/dL) at weeks of 48, 98 and 144.
	 The percentage of change from baseline in serum phosphate at weeks of 48, 98 and 144.
	 Change from baseline in phosphorus values at weeks of 48, 98 and 144
Exploratory Objectives	
To explore the Bone Mineral Density (BMD) change among overall and sub-group CHB patients during TDF treatment	Percentage of BMD change from baseline at weeks of 48, 96, and 144
To investigate predictors of effectiveness among CHB patients who receive long-term	Baseline or on-treatment predictors (e.g. baseline characteristics, etc).
TDF treatment	Treatment effectiveness, including CVR, HBeAg loss and/or HBeAg, transaminage normalization
To explore risk factors of safety among CHB patients who receive long-term TDF treatment	Baseline or on-treatment risk factors (e.g. baseline characteristics, co-morbidities, and concomitant treatment etc).
	Renal impairment, including eGFR decline and serum phosphate
	Bone impairment, including BMD decline

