12. STUDY LIMITATIONS

This is a China-based multi-centre, prospective, longitudinal, non-interventional study conducted in a real-world setting in order to investigate long-term effectiveness and safety of TDF among Chinese CHB patients to guide clinical practice. The absence of comparison group is one of the major limitations to this study, which can be mitigated by a historical comparison leveraging previous trial data from literature or in-house alternatively. The mixing of the new initiator and on-treatment patients is another limitation, which may complicate the analysis due to varied treatment duration and inconsistent baseline information. Potential solutions include setting restriction on the inclusion criteria to the patients who have already started TDF prior to the entry of study in line with those of new initiators.

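### Section 9.3.2 reports CVR and transaminase normalization over all analysed patients, so new response is mixed with a status some patients already had at TDF start

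*Protocol*

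**What the plan says.** Protocol section 9.3.2 opens its effectiveness list by stating that "the following estimates will be summarized for the overall analysis population and subpopulations". The list includes CVR at the three time points and "The proportion of patients who achieve transaminase normalization at weeks of 48, 96, and 144". Neither item has a baseline condition. The HBeAg item in the same list does: it is confined to patients who are HBeAg positive.

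Section 9.2 says the main population will "consist of all consented participants who have the requested baseline data and at least one post-baseline assessment data". Section 9.1.2 describes the endpoint as "the proportion of subjects who achieve the CVR (i.e. HBV-DNA undetectable) at weeks of 48, 96, and 144", which is a status at a visit and not a change from a detectable starting value.

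Sections 6.1 and 6.2 set no HBV DNA or ALT threshold; the indication for treatment is left to the physician. Earlier treatment with other NUCs is not an exclusion. The subgroup list in 9.3.2 names "receipt or no-receipt of previous treatment with other NUCs", baseline HBV DNA level, and baseline ALT relative to the upper limit of normal (ULN).

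Table 2 in section 4 also lists "Time to CVR, defined as time from baseline to the first occurrence of CVR", qualified by the words if applicable. It is not in the 9.3.2 list; its Kaplan-Meier and Cox analyses appear under the exploratory section 9.3.4.2.

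**The concern.** A patient who switches from another NUC with HBV DNA already undetectable, and stays undetectable, counts as having achieved CVR. The overall proportion then depends partly on how many such patients enrol. Section 9.3 plans tests between subgroups. A higher CVR in NUC-experienced or low-DNA patients could reflect their starting status and be misread as a predictor of response to TDF. The same applies to a time-to-CVR curve in which some patients have the event at or near time zero.

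For transaminases, a patient with normal values at TDF start cannot normalize in the ordinary sense. Such a patient is counted either as an automatic success or as an unavoidable failure, and the protocol does not say which. In the planned subgroup with normal baseline ALT, the proportion carries no information about normalization under either rule.

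**Working it through.** **1. The plan's own precision.** Inputs from section 9.1.2: N = 2000, 35% loss and discontinuation, CVR 80%, 95% interval.
- Completers: 2000 × 0.65 = 1300.
- Half-width: 1.96 × √(0.80 × 0.20 / 1300) = 0.0217. The stated 2.2 points is reproduced. The arithmetic is sound; the question is which patients the 80% describes.

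**2. Mixture for CVR.** Let f be the share undetectable at TDF start, m the share of those still undetectable at week 144, and r the CVR among patients detectable at TDF start. Then overall CVR = f·m + (1 − f)·r, and the shift from r is f·(m − r), upward whenever m exceeds r. The protocol gives neither f nor m, so both are assumed. With r = 0.80 and m = 0.98:
- f = 10%: 0.098 + 0.720 = 81.8%
- f = 20%: 0.196 + 0.640 = 83.6%
- f = 30%: 0.294 + 0.560 = 85.4%

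**3. The same relation in reverse.** Section 9.1.2 assigns 80% to patients overall. If 80% is the overall result, then r = (0.80 − f·m)/(1 − f). With m = 0.98, r is 78.0%, 75.5% or 72.3% for f = 10%, 20% or 30%.

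**4. When the shift exceeds the planned precision.** Setting f·(m − 0.80) = 0.022:
- m = 1.00: f = 0.022/0.20 = 11%
- m = 0.98: f = 0.022/0.18 = 12%
- m = 0.95: f = 0.022/0.15 = 15%

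At f = 5% and m = 0.98 the shift is 0.05 × 0.18 = 0.9 points, well inside the interval.

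**5. Transaminase normalization.** Let g be the share normal at TDF start and q the share of the others who normalize. Counting the already normal as successes (supposing they stay normal) gives g + (1 − g)·q. Counting them as failures gives (1 − g)·q. The gap equals g, whatever q is. For illustration only, with g = 40% and q = 75% (neither in the protocol): 0.40 + 0.45 = 85% against 45%, while the proportion among patients able to normalize is 75%.

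**6. Precision after restriction.** Assume the same 35% loss in both groups and 80% CVR among patients detectable at TDF start:
- f = 20%: n = 1300 × 0.80 = 1040, half-width 1.96 × √(0.16/1040) = 0.024
- f = 30%: n = 1300 × 0.70 = 910, half-width 1.96 × √(0.16/910) = 0.026

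**The case against.** The strongest reply is that undetectable HBV DNA at week 144 among everyone treated is a legitimate quantity for a descriptive study of TDF in routine practice, and that keeping a switched patient suppressed is itself effectiveness. That stands. A reader might infer that the CVR proportion fails to measure TDF effectiveness; the protocol does not support so strong a reading. It measures a blend that needs to be separated.

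Second, section 9.3.2 already plans results by baseline HBV DNA, by ALT relative to ULN, and by prior NUC use. This helps considerably. But no detectable/undetectable cut is fixed for HBV DNA, and the overall figures remain unrestricted.

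Third, endpoint rules are often left to the analysis plan, and section 9.3 refers to a Reporting and Analysis Plan that is not at hand. The word normalization also suggests an abnormal start. Both are fair, and that plan may already settle the matter. Yet the protocol names the overall population for these endpoints while writing the restriction into the HBeAg item beside them, so it should be made consistent.

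Fourth, time to CVR is analysed as exploratory, and its qualifier may permit leaving out patients already undetectable. That wording is ambiguous, so this part is only a clarification.

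**Conclusion.** The point holds in limited form. As written, the headline CVR combines achieved with maintained suppression, and the normalization proportion is not interpretable while patients already normal are in its denominator. The likely direction for CVR, read as new response, is upward. Its size rests on an assumed share suppressed at TDF start and on assumed maintenance of 95% to 100%, and it may be negligible if few suppressed patients enrol. The normalization problem depends less on assumptions, since the ambiguity equals the share already normal.

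Two further readings are tempting but unsupported. A reader might infer that patients already on TDF at entry cause the inflation. Note 6 to the Schedule of Activities anchors their follow-up to actual TDF initiation, and section 6.1 requires laboratory results from that time, so they are not the source as such. A reader might also infer an error because the phase III rates in section 3.2 use 69 IU/ml while CVR here means undetectable. The 20 IU/ml limit is given only for pre-entry records in inclusion criterion 4. Section 12 says only that the lack of a comparator "can be mitigated by a historical comparison leveraging previous trial data from literature" or in-house data, without naming a trial or rate.

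**What to change.** In section 9.3.2, and correspondingly in the Reporting and Analysis Plan:

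- Restrict transaminase normalization to patients with ALT (or AST) above ULN at TDF start.
- Keep the overall proportion undetectable at weeks 48, 96 and 144. Report beside it CVR among patients with detectable HBV DNA at TDF start, and maintained CVR among those undetectable at TDF start.
- Fix detectable versus undetectable as a cut in the planned HBV DNA subgroup.
- In section 9.3.4.2, limit the time-to-CVR Kaplan-Meier and Cox analyses to patients detectable at TDF start.
- Optionally, add a row for HBV DNA below 69 IU/ml if the phase III rates are used for a historical comparison.

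Settle this before the first week-48 cut-off analysis, so that the denominator is not chosen with results in view. No new data are needed: section 7.2 already collects HBV DNA, ALT and AST at TDF start. The cost is smaller denominators, with half-widths of about ±2.4 points if 20% start suppressed and ±2.6 if 30% do, against ±2.2 planned. The normalization endpoint likewise loses the patients already normal, a share the protocol does not give.
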